9.7.5 Feasibility Assessment for Further Exploratory Analyses

To understand the VE on different variants of the coronavirus, we will describe the VE by a combination of region and time period that aligns with best knowledge of when and where new variants of the virus were present according to available data sources and explore mechanisms for future individual level studies.

To study the VE among people in long term care (LTC) or assisted living facilities in the subset of subjects with data available on household key, median household age (>60), and number of residents (9 or more) and can be linked to the Care Quality Commission register, which lists residences where a degree of nursing care is provided. These variables will be used as a proxy to identify individuals receiving LTC at home or at specialized facilities.

9.7.6 **RAVEN Extension Analyses (Other than VE)**

9.7.6.1 **Populations at Risk and Predictors of Having Boosters**

The risk profile of the population at risk of COVID-19 due to either being ineligible for COVID-19 vaccines or due to suboptimal vaccine response (i.e. immunocompromised individuals) will be described. Specific subgroups (including their size) may be identified. AI/ML methods will be applied to explore the risk profile of the population at risk of COVID due to suboptimal vaccine response, and thus who may be more likely to experience breakthrough cases. A breakthrough case is defined as a person who has a positive virology test for the COVID-19 virus 14 or more days after their second vaccination (CDC definition (CDC, 2021)). We will consider predictions of breakthrough cases of SARS-CoV2 infections and clinically significant breakthrough infections (i.e. the primary outcomes), the identification of susceptible sub-populations and predictions of the time to vaccine waning with respect to these outcomes. People who are immunocompromised are the primary population of interest. AI/ML methods will also be used to identify predictors of receiving AZ boosters.

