Secondary: To assess the real-world effectiveness of other COVID-19 vaccines in people vaccinated who received at least one dose; overall, and by number of doses, by age group, by comorbidity status, by time period after each dose, and by interval between the doses.

RAVEN extension objectives:

- 1. To describe the risk profile of the population at risk due to being ineligible for COVID-19 vaccines due to having suboptimal vaccine response (and thus more likely to have a breakthrough case), predict breakthrough cases and their time to vaccine waning, and describe the predictors of accepting AZ boosters. People who are immunocompromised are the primary population of interest, in our exploration of suboptimal vaccine response.
- 2. To conduct an analysis of COVID-19 and long COVID HCRU and health care cost for the whole population and for risk groups identified as having a suboptimal vaccine response.

- 3. To explore VE against the different SARS-CoV-2 variants.
- 4. To assess the effectiveness of the Oxford/AstraZeneca COVID-19 vaccine against any positive SARS-CoV-2 test, medically attended COVID-19 and rate of emergency department visit associated with COVID-19.
- 5. To assess the effectiveness of the Oxford/AstraZeneca COVID-19 vaccine and other COVID-19 vaccines in people vaccinated with booster/other additional doses.
- 6. To assess the effectiveness of heterologous dosing (including at least one Oxford/AstraZeneca COVID-19 vaccine)
- 7. To estimate the impact of vaccination on household incidence/transmission
- 8. To estimate the impact of vaccination on long COVID

Methods:

Study design: Secondary data analysis using a retrospective cohort design

Population: The study population is people in England who have received at least one dose of the Oxford/AstraZeneca COVID-19 vaccine (the AstraZeneca vaccine arm) or at least one dose of other COVID-19 vaccines (the other COVID-19 vaccine arm) and people in England who were not vaccinated with any COVID-19 vaccine during the same time period (concurrent control arm). All study participants are eligible for COVID-19 vaccination based on age.

Variables

Exposure(s): The main exposure is whether a person was vaccinated with the Oxford/AstraZeneca COVID-19 vaccine or with any other COVID-19 vaccine versus not vaccinated with any COVID-19 vaccine.

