9.1 Study Design – General Aspects

The effectiveness objectives will be addressed through a retrospective cohort study using linked secondary databases in England accessed through ORCHID and NHS Digital's TRE. Persons vaccinated with Oxford/AstraZeneca COVID-19 vaccine or another COVID-19 vaccine will be compared to matched persons not vaccinated with any COVID-19 vaccine for occurrence of study outcomes.

Due to England's vaccination campaign starting with the older age group, as of March 22 2021, over 90% of people 70 years of age or older were vaccinated with at least one dose of any COVID-19 vaccine (Public Health England, 2021). Therefore, it is expected that the concurrent control arm will have considerable challenges. A greater proportion of younger people might be included who may have lower hospitalization and death (particularly because the Joint Committee of Vaccination and Immunisation (JCVI) recommended early vaccination of people 16 to 64 years with comorbidities). Additionally, people receiving terminal care and those who do not engage much with the health system may also be included. For these reasons, the concurrent control arm is matched with the vaccine arm by age and other characteristics. Events' rates will also be stratified by age groups (e.g. 12-15,16-49, 50-64, 65-69, 70-79, 80+).

We will also explore how COVID-19 vaccination in England coincided with the 3rd wave of COVID-19 and any subsequent wave that may occur. For this analysis, we will include vaccination data periods beyond February 2021.

There have been changes in the age groups vaccinated and the introduction of booster doses. The Moderna and Pfizer BioNTech vaccines have been licenced for children (Medicines and Healthcare products Regulatory Agency (a & b), 2021) and booster doses were introduced in the autumn of 2021. For these reasons the analyses will be extended to include the 12–16-year-old age-group and any booster vaccination (9)(Department of Health and Social Care, 2021). Finally, the UK COG has centralised data on COVID-19 variants allowing VE to reported by variant.

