9.2.4 Participant Follow-up

For the vaccinated and concurrent control arms, study participants will be followed from the index date to the end of the study, loss to follow-up (deregistration), vaccination (for unvaccinated controls), vaccination of the matched control (for vaccinated people), or death, whichever is earlier.

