9.7 Data Analysis

9.7.1 Statistical Methods – General Aspects

A detailed SAP will be developed for this analysis. The SAP may modify the plans outlined in the protocol; any major modifications of primary endpoint definitions or their analyses would be reflected in a protocol amendment. For all study designs, p-values will be quoted to two decimal places, unless they are less than 0.001 (whereby the p-value will be given as < 0.001) or between < 0.005 and > 0.001, in which case they will be stated to three decimal places. Parameter estimates will be reported with 95% CIs. All statistical tests are 2 sided and with a 5% significance level.

A CONSORT 2010 Flow Diagram of the study population detailing each step of the inclusion and exclusion criteria applied will be generated. As indicated in section 9.4, to obtain the most followup data, the primary analysis will include all HES data until 8 weeks prior and all raw hospitalization data (SUS) from 8 weeks to 2 weeks prior database lock. A sensitivity analysis including only HES data, therefore a shorter follow-up for hospitalization, will also be done.

For the concurrent control arm, each week starting from 8th December 2020, we will match all newly vaccinated persons in a 1:1 ratio to unvaccinated controls (Dagan et al, 2021). Newly vaccinated persons will be eligible for inclusion in the study, even if they will have previously been selected as a control. We will match vaccine recipients and controls on variables associated with the probability of both vaccination and infection or severity of COVID-19: age (study defined age bands), gender, general practice, (or NHS Region), and comorbidity as defined by CMMS quartile. We will exact match each week (if feasible). To assess the quality of matching, love plots will be created showing the mean standardized difference between each vaccinated cohort (AstraZeneca or other vaccine cohort) and the comparator cohorts in participants' characteristics. If important differences are observed, the matching criteria will be refined.

The demographic and characteristics of study participants in each vaccine arm and its respective control arm at baseline will be determined during the 12-month period before index date using the measurement closest to index date.

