Summary tables of all patient characteristics and end points indicated in section 9.3.2 will be created for both the before and after matching situation to provide insight in population characteristics as well as in errors and missingness. Categorical variables will be checked on meaningful categories and frequencies. It is not anticipated that categories will have too low frequency. Pooling will be considered when the frequency for a category becomes below 1000.

Continuous variables will be summarized in terms of min, max, interquartile range, median and mean to get insight in these variables, but also to provide a first indication of use of same unit across the database and to obtain a first impression about possible transformations needed. Missing values will be considered in detail. If the percentage of missingness is below 10%, complete case analyses will be performed. When exceeding 10%, multiple imputation will be run additionally based on the total dataset.

For each outcome event, the summary tables will present for each study cohort the number of first events, total person-years for the event and number of first events per person-years (rate), the RR and the VE which is calculated as 1 - RR. This will also be provided per age group and per frailty score where further stratification/subgroups are indicated below. Finally, VE will also be provided in shorter periods after dose 1, and between the doses, and presence of comorbidities.

Poisson regression with offset for time at risk will be used to estimate rates using the matched dataset, adjusting for the matching variables and BMI, smoking, prescribed medications, and frailty score, which are known to increase risk of hospitalization and death and are likely associated with vaccination.

Checks on linearity for continuous variables will be performed. In order to evaluate interactions of independent variables with the exposure (i.e. vaccinated/comparator), continuous variables will be categorized and the VE will be tabulated per category. For variables for which the maximum and minimum VE across categories is more than 10% different, interaction effects with the exposure will be taken into account in the Poisson model. For interactions among independent variables that are not the exposure, interaction variables will be created. Forward selection is performed, and interaction variables will be included when the computed VE changes with more than 10%.

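### Section 9.7.5 uses region and calendar period as a proxy for variant without holding time since last dose fixed, so a descriptive VE for a later variant period can fall through waning alone

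*Protocol*

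**What the plan says.** Extension objective 3 in the synopsis (Section 4) is: "To explore VE against the different SARS-CoV-2 variants". The only VE method given for it is in 9.7.5, which will "describe the VE by a combination of region and time period that aligns with best knowledge of when and where new variants" were present and will "explore mechanisms for future individual level studies". Sections 9.1 and 9.3.2 name the UK genomics consortium as the variant source, and 9.7.2 lists variant as a possible stratum among people with COVID-19. None of these is turned into an individual-level VE analysis.

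On entry, 9.7.1 states: "each week starting from 8th December 2020, we will match all newly vaccinated persons in a 1:1 ratio to unvaccinated controls". Section 9.1 explains the order of vaccination ("Due to England's vaccination campaign starting with the older age group") and adds: "There have been changes in the age groups vaccinated and the introduction of booster doses". Under 9.2.4, follow-up of a vaccinated person can end at "vaccination of the matched control (for vaccinated people), or death, whichever is earlier".

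The Poisson model in 9.7.1 is fitted "adjusting for the matching variables and BMI, smoking, prescribed medications, and frailty score". Time since dose and dose number are not in that list. Stratification by time after each dose is announced in 9.3.1. The bands listed in 9.7.2 cover dose 1 only and stop at day 84, although other combinations are allowed. Neither section links these strata to 9.7.5.

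**The concern.** Calendar period stands in for variant, but it also tracks how long ago people were vaccinated. Weekly matching puts each vaccinated person and control in the same calendar week. It cannot balance time since dose, which exists only for the vaccinated. Person-time in a later variant's period is therefore, on average, further from the last dose unless new vaccination or pair censoring removes the older follow-up.

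The protocol does not treat waning as hypothetical. The synopsis gives it as a reason for boosters, and 9.3.2 lists time to waning as an outcome. A table of VE by variant period would then mix two explanations for a lower figure: a different variant, or older vaccination. If doses were pooled, boosters entering late could push the other way and mask a real difference. The limitations in 9.9 say that variant data are lacking but do not mention this mixing.

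**Working it through.** The protocol gives no event count, power or VE figure for this analysis, so there is nothing of its own to reproduce. The check asks what period VE would look like with **no variant effect**.

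**Formula.** With 1:1 pairs, VE in period p is the sum over time-since-dose bands k of w(p,k) × VE(k). Here w(p,k) is the share of expected control events in period p that falls in band k.

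**Simple illustration (all inputs assumed).** VE is 85/80/75% in early, middle and late bands. The mix is 75/20/5% in the first period and 15/35/50% in the second.
- First: 0.75×85 + 0.20×80 + 0.05×75 = 83.5%.
- Second: 0.15×85 + 0.35×80 + 0.50×75 = 78.25%.
- False gap: 5.25 points. With VE of 90/80/70% the figures are 87.0% and 76.5%, a gap of 10.5 points.

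**Adding the rollout and pair censoring.** From the protocol: weekly entry from 8 December 2020, oldest first, 1:1 pairs, end of follow-up when the control is vaccinated, and one-dose exposure counted from day 22. Assumed:
- Equal numbers per age group, entering evenly: old in weeks 4–11, middle-aged in weeks 12–21, young in weeks 22–33.
- Control event rates of 8:3:1 (old : middle-aged : young).
- Period A before week 22, period B weeks 26–43.
- Bands of under 12, 12 to under 20, and 20 or more weeks since dose 1.
- A fraction c of pairs lost each week, so that (1 − c)^t remain after t weeks.

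Example at c = 13%:
- Period A mix 91.2/8.8/0%: 0.912×85 + 0.088×80 = 84.6%.
- Period B mix 40.7/31.4/27.9%: 0.407×85 + 0.314×80 + 0.279×75 = 80.6%.

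| Weekly pair censoring | VE period A | VE period B | False gap (points) |
|---|---|---|---|
| 0% | 84.0% | 76.8% | 7.1 |
| 3% | 84.1% | 77.5% | 6.6 |
| 8% | 84.4% | 79.0% | 5.4 |
| 13% | 84.6% | 80.6% | 3.9 |
| 20% | 84.8% | 82.7% | 2.0 |

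The 13% row corresponds to the 91% uptake at ages 65 and over by 7 April 2021 in Section 9.5. That is 120 days, or 17.1 weeks, after 8 December 2020, and 1 − 0.09^(1/17.1) = 13%. Counting follow-up from the day of vaccination, or compounding the censoring differently, moves this row to between about 3.5 and 4.2 points. The gap scales with the waning step, so 90/80/70% doubles every gap in the table.

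**Is it removed by what is planned?** A Poisson model with offset, adjusted for age and period, was fitted to expected counts under the same rollout with censoring of 0–8% a week. The ratio of rate ratios, period B to period A, should be 1.00.

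| Assumed VE by band | Period A | Period B | Ratio of rate ratios | With time-since-dose strata |
|---|---|---|---|---|
| 90/90/90% | 90% | 90% | 1.00 | 1.00 |
| 90/85/80% | 89% | 82–84% | 1.5–1.65 | 1.00 |
| 90/80/70% | 88–89% | 74–78% | 2.0–2.2 | 1.00 |
| 90/75/55% | 87–88% | 62–69% | 2.6–2.9 | 1.00 |

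Age adjustment does not remove the false difference; time-since-dose strata do.

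**Age mix on its own.** With VE of 80/90/92% in old, middle-aged and young and no waning, period A gives 81% and period B 83–84%. That is a false rise, and an age-by-vaccination interaction returns the ratio to 1.00.

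**The case against.** The strongest reply is that 9.7.5 is a feasibility section that promises description and leaves individual-level work to later studies. That stands. A reader might infer an inflated false-positive rate for a claim that a later variant escapes the vaccine. The protocol plans no test of equal VE between variants and makes no such claim, so no error rate can be attached to it.

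Second, the crossing of strata may be set out in the SAP, to which 9.7.2 refers and which is not shown. It may be. But the protocol itself fixes the proxy and the covariate list, and it is that pairing which mixes variant with waning.

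Third, dose number is partly handled: 9.3.1 separates one-dose, two-dose and additional-dose person-time, and boosters have their own objective. That stands, so the main gap is time since last dose.

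Fourth, a reader might blame the changing age mix. The documents do not support that as a main cause. Age is matched and adjusted, and 9.7.1 adds an interaction with vaccination where VE differs by more than 10% across categories. Time since dose is not among the variables listed there.

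Fifth, region can help: where a variant reached regions at different times, regions can be compared in the same weeks. The check above has no region dimension. Sixth, censoring at the control's vaccination shrinks the gap, as the table shows, though it would slow once mainly persistent decliners remain as controls. These last two points reduce the problem without removing it.

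**Conclusion.** The point holds as a limited one. As written, VE by region and period cannot separate variant from time since last dose, and a later variant period can show lower VE with no variant effect. At assumed VE of 85/80/75% the false gap is roughly 2 to 7 points over weekly pair censoring of 20% down to 0%; it is larger with steeper waning and absent without waning. Those figures rest on assumed VE values, entry weeks, event rates and period boundaries, and the documents do not fix the size. Age mix is a minor matter. The primary VE is unaffected, and it would be wrong to read this as a flaw in the main analysis. The change is still worth making, because the period figures are meant to inform VE by variant and the vaccination dates and dose numbers needed are already held (9.3.1, Table 4).

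**What to change.** In 9.7.5, present region-period VE within bands of time since last dose and by dose number, or add vaccination-by-time-since-dose terms to the Poisson model for this analysis. Extend the 9.7.2 bands beyond 84 days and to dose 2 and boosters; the listed ones do not reach the follow-up where the problem lies. Use same-calendar-time contrasts between regions where they exist. Make any statement about differences between variants only at equal time since last dose and equal dose number. Add to 9.9 that unstratified period VE cannot separate variant from waning.

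No new data are needed. The cost is wider intervals and some empty cells, for example long time since dose in the earliest variant period. Those cells show where the two explanations cannot be told apart.

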9.7.6.2 Health Care Resource Use and Health Care Cost Related to COVID-19

The objective of the economic analysis will be to estimate incremental health service use and incremental health service costs associated with receipt of at least one dose of the Oxford/AstraZeneca COVID-19 vaccine (the AstraZeneca vaccine arm) or at least one dose of other COVID-19 vaccines (the other COVID-19 vaccine arm) over the short (one and three months of follow-up) and medium term (six months of follow-up) and to disaggregate incremental costs by cost category. Our comparator groups and their construction will mirror those proposed for the statistical analyses, namely: (i) the AstraZeneca vaccine arm; (ii) the other COVID-19 vaccine arm; (iii) the concurrent control arm. The approaches to matching participants based on age group, gender, region, comorbidity status and practice, and to defining the date of study entry, will mirror those proposed for the statistical analyses.

Cumulative health care service use and health care costs covering primary and secondary health care services over 1 month, 3 months and 6 months of follow-up will be estimated using data extracted from the data assets listed in Section 9.4, and grouped by the following clinical settings and resource categories:

- Primary care consultations;
- Primary care prescriptions;
- Primary care medical tests and investigations;
- Hospital outpatient attendances and procedures;
- Hospital A&E (emergency department) attendances without admission
- Hospital admissions, inpatient, and day cases.

Primary and secondary care services will be valued by attaching unit costs derived from national compendia to resource inputs. All costs will be expressed in pounds sterling and valued at 2021 prices with unit costs estimated at earlier price dates inflated to 2021 prices using the NHS Hospital and Community Pay and Prices Index.

Characteristics of each comparator group will be compared using t-tests for continuous variables and chi-square tests for categorical variables. Initial exploration of the data will be conducted to guide selection of the appropriate analytic strategy. Inverse probability weighted GEE (Salazar et al., 2016) will be used to model non-linear trends in healthcare service use and costs over time, accounting for missing data, and adjusting for the matching variables and BMI status, smoking status, and frailty score. In the models, the total follow-up period will be divided into time intervals and interval-specific weights calculated as the inverse cumulative product of the probability of being observed up to a given interval using the method of van der Wal and Geskus (2011). Inverse probability weighting ensures that observations with a high probability of being missing (for example costs incurred in the later months of follow-up) are given more weight than observations with a low probability of being missing (for example costs incurred in the earlier months of follow-up) (Glick et al., 2015).

Adjusted estimates of cumulative healthcare utilisation counts, lengths of stay and costs, and between-group difference in counts, length of stay and costs, will be obtained from the regressions by summing interval-specific estimates over the time period of interest, a strategy originally reported by Lin (2000). Standard errors and confidence intervals around the mean estimates will be obtained via the robust variance/sandwich estimator, which provides a degree of robustness to departures from normality of errors and misspecification of the GEE working correlation matrix. An alternative approach for estimating standard errors and 95% confidence intervals is through the use of non-parametric bootstrapping. This would involve randomly sampling individual patients with replacement from the data to generate, for example, 1000 replicate datasets, and then fitting regression models to each replicate dataset and calculating adjusted bootstrap estimates of cumulative counts, lengths of stay and costs and the respective between-group differences. However, we recognise that the non-parametric bootstrap method can be computationally expensive for large sample applications such as ours. As a sensitivity check of the results generated by our primary modelling approach, we will therefore also apply the nonparametric bootstrap method to a smaller sample of data to obtain bias-corrected standard errors and confidence intervals. For completeness, the analyses will be repeated by restricting to patients with complete data over 1, 3 and 6 months of follow-up. The approaches to handling potential confounding will mirror those adopted by the statistical analyses. The analyses will also be repeated by the subgroups pre-specified by the statistical analyses.

We will also report the health care resource use and health care costs by COVID-19 risk group, using the JCVI risk group classification.

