9.2.2 Inclusion Criteria

The study population is required to meet the following inclusion criteria:

1. For the vaccinated arms:

- Any COVID-19 vaccination at the index date
- Have continuous data coverage for the COVID-19 infection datasets, i.e. Second Generation Surveillance System (SGSS) and National Pathology Exchange (NPEX) from their initiation for history of prior COVID-19 infection
- Have continuous data coverage in other linked databases for a minimum of 12 months prior to the index date for assessment of baseline variables including socio-economic status, comorbidities, and follow-up of outcome events.

2. For the control arms:

- Eligible for any COVID-19 vaccination based on age at the index date for the concurrent control individuals.
- Have continuous data coverage for the COVID-19 infection datasets, i.e. SGSS and NPEX from their initiation for history of prior COVID-19 infection
- Have continuous data coverage in other linked databases for a minimum of 12 months prior to the index date for assessment of baseline variables including socio-economic status, comorbidities, and follow-up of outcome events.
- People who have not (yet) received any COVID-19 vaccine (Oxford/AstraZeneca, Pfizer, or Moderna COVID-19 vaccine) recorded in their GP record or in NIMS. They will be used as concurrent controls. However, they will be censored at date of vaccination and, then may re-enter the study as newly vaccinated individuals.

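### The use and cost GEE omits each person's own pre-index health-care use and cost, so differences that survive matching can be reported as incremental to vaccination

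*Protocol*

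**What the plan says.** The aim of the economic analysis in section 9.7.6.2 is "to estimate incremental health service use and incremental health service costs associated with receipt of at least one dose", for the AstraZeneca and other-vaccine arms, over 1, 3 and 6 months, with the concurrent unvaccinated arm as comparator. The model is an inverse probability weighted GEE, "adjusting for the matching variables and BMI status, smoking status, and frailty score". Its weights are the "inverse cumulative product of the probability of being observed up to a given interval". The section adds: "The approaches to handling potential confounding will mirror those adopted by the statistical analyses".

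The matching variables in section 9.7.1 are "age (study defined age bands), gender, general practice, (or NHS Region), and comorbidity as defined by CMMS quartile". The effectiveness model in the same section is a Poisson regression "adjusting for the matching variables and BMI, smoking, prescribed medications, and frailty score".

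On the data available, section 9.2.2 sets this criterion for both the vaccinated and the control arms: "Have continuous data coverage in other linked databases for a minimum of 12 months prior to the index date for assessment of baseline variables". On the expected make-up of the controls, section 9.1 names people receiving terminal care and says that "those who do not engage much with the health system may also be included". Section 9.11.1 accepts that people who choose vaccination may differ from those who do not.

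**The concern.** Health-care contact is the outcome here. A person's earlier contact and cost are the natural baseline value of that outcome and would be expected to predict it. People who rarely consult will tend to go on consulting rarely whether or not they are vaccinated, and people near the end of life will tend to go on using many services. Age band, gender, practice or region and a multimorbidity quartile capture part of this, but none of them measures the rate of contact. The frailty score could help, but Table 6 says it exists only from age 65, so younger adults lack that proxy.

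If the arms still differ in prior use after matching, the GEE has no term to absorb the difference and carries it into the incremental estimate. A non-zero incremental use or cost could then appear when vaccination changed nothing, or a real change could be hidden. A national sample does not help, because it makes a small spurious difference statistically clear.

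**Working it through.** **1. Is prior use or cost anywhere in the plan's control of confounding?**

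| Place in the protocol | Content relevant here | Prior use or cost? |
|---|---|---|
| 9.7.1, matching | age band, gender, practice or region, CMMS quartile | No |
| 9.7.6.2, GEE covariates | matching variables, BMI, smoking, frailty | No |
| 9.7.1, Poisson model (mirrored) | the same plus prescribed medications | No |
| 9.3.3, Table 6 | demographics, comorbidity, non-COVID vaccination, medication, frailty and others | No |
| 9.7.3, sensitivity analyses | data source, prior infection, 14-day window, care homes | No |
| 9.7.6.2, weights | probability of being observed | No; missing follow-up only, not receipt of vaccine |

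The nearest item in Table 6 is non-COVID vaccination history, a possible marker of engagement. It is in neither model's covariate list. Prior use is also not among the listed characteristics, so the love plots of 9.7.1 would not necessarily show an imbalance in it.

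**2. Is there a figure to reproduce?** No. The protocol gives no sample size, effect size, imbalance or correlation for use or cost. What follows is an illustration on assumed inputs.

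**3. Illustration with no true vaccine effect.** Let U be engagement within strata of the protocol's covariates, differing by d SD between arms. Let pre- and post-index use each have unit variance within arm and correlation r through U.

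- Spurious difference without pre-index use in the model: √r × d.
- Spurious difference after adjusting for pre-index use: √r × d × (1 − r).

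| r | d | Without | With |
|---|---|---|---|
| 0.3 | 0.05 | 0.0274 | 0.0192 |
| 0.3 | 0.20 | 0.1095 | 0.0767 |
| 0.5 | 0.10 | 0.0707 | 0.0354 |
| 0.7 | 0.05 | 0.0418 | 0.0125 |
| 0.7 | 0.20 | 0.1673 | 0.0502 |

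Over r = 0.3 to 0.7 and d = 0.05 to 0.20, the spurious difference is 0.027 to 0.167 SD without adjustment and 0.013 to 0.077 SD with it. The fraction removed equals r, so 30% to 70%.

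Simulation check (200,000 per arm, d = 0.1, r = 0.3, 0.5, 0.7): 0.051, 0.077, 0.084 without and 0.035, 0.041, 0.027 with. The Monte Carlo standard error is about √(2/200,000) = 0.003, so these agree with the formula to within about two standard errors.

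**4. If prior use is itself the confounder.** The bias is then r × g, where g is the pre-index gap in SD: from 0.3 × 0.05 = 0.015 to 0.7 × 0.20 = 0.14 SD. Adjustment removes all of it.

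**5. Does sample size protect?** With an assumed 100,000 per arm, the standard error of a difference is √(2/100,000) = 0.0045 SD. The smallest unadjusted value gives 0.0274 / 0.0045 ≈ 6.1, so it would be significant at the two-sided 5% level with probability about 1.00.

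**The case against.** Five objections deserve an answer.

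- **Outcome scope.** The heading of 9.7.6.2, the outcome list in 9.3.2 and Table 3 tie use and cost to COVID-19 or long COVID. If that restriction holds, the same-category value before index is close to zero, because 9.2.3 excludes prior infection from the primary analysis and the economic comparator groups mirror the effectiveness ones. Prior all-cause use would then be a proxy for engagement rather than the outcome's own baseline. This stands as a condition on the fix. The resource categories in the body of 9.7.6.2 carry no such restriction, so the protocol leaves the matter open.
- **Direction and certainty.** A reader might infer that controls are selected for low contact and that vaccination will therefore look costly. The documents do not support this. Section 9.1 says only that such people may be included, names terminal-care patients alongside them, and gives matching as its response. Controls may also simply be not yet vaccinated, since 9.2.1 lets them re-enter as vaccinated. Only imbalance left after matching matters, and its sign is unknown.
- **Size.** Any percentage bias for this study would only return the imbalance assumed for it. The figures above are illustrative for that reason.
- **Room to adapt.** Section 9.7.6.2 foresees initial exploration to guide strategy, and 9.7.1 lets the SAP modify plans and matching be refined if important differences appear. These clauses permit the addition but do not commit to it, and the protocol does state a specific covariate list.
- **Prescribed medications.** A reader might infer that the cost analysis drops this confounder. The mirroring sentence may well bring it in. What stands is a mismatch between the GEE list in 9.7.6.2 and the list in 9.7.1.

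**Conclusion.** The point holds for section 9.7.6.2. The protocol names a covariate set for the use and cost GEE that leaves out pre-index use and cost. It requires the data from which they could be derived, and it anticipates arm differences in engagement. Neither the weights nor the mirrored effectiveness model makes up for the omission. Residual differences in prior use can therefore appear as incremental use or cost of vaccination, in either direction.

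The protocol does not allow the size to be derived. The SD ranges rest on assumed correlations and gaps and on a simple linear model. They show that the bias need not be negligible at this scale, and that adjustment reduces it but does not necessarily remove it. With 100,000 per arm, the remaining 0.0125 SD in the most favourable case would still be significant with probability about 0.80.

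A reader might extend the same conclusion to the all-cause hospitalization and ICU outcomes. Prior admissions are indeed absent from the Poisson model, but no size has been worked out for those outcomes, and comorbidity and frailty may already cover part of the difference. For them it is an optional refinement.

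**What to change.** - In the GEE paragraph of 9.7.6.2, add to the covariates the person's own health-care use and cost in the same resource category over the 12 months before index.
- State whether the outcome is all-cause or COVID-19-related use. If it is COVID-19-related, enter prior all-cause use as a proxy for engagement instead.
- Show pre-index use and cost by arm in the love plots of 9.7.1.
- Align the GEE list and the mirroring sentence in 9.7.6.2 with the Poisson covariates in 9.7.1 on prescribed medications.
- Optionally, add admissions in the prior year to the all-cause hospitalization model.

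The cost is a few sentences, plus deriving pre-index counts from the linked data sources and applying unit costs to the pre-index year. One drawback remains: indexing starts in December 2020, so the look-back year of early entrants falls largely in 2020, when use was disturbed by the pandemic. Prior use will be a noisier guide for them.
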